[name], former Assistant Secretary of DHHS, has proposed a Health Literate Care Model based on the chronic care model.^{30,31} The model encourages both patients and providers to be activated and engaged and suggests that improving health outcomes relies on patients' full engagement. Our strategy, in combination with PCMH standards achieved by each clinic, and previous clinic training by [name] in implementing health literacy strategies recommended in the Agency for Health Care Quality and Research's (AHRQ) Health Literacy Universal Precautions Toolkit³² address many of the attributes included in this model: 1) assuming all patients are at risk of not sufficiently understanding their disease or self- management; 2) providing clear communication following plain language principles and easy to read, culturally appropriate materials, 3) confirming and ensuring patients understand via the '*teach back*' technique, 4) providing close follow-up with patients using a health coach, 5) incorporating provider health literacy training and point-of-care clinical reminders for medication reviews, 6) use of an electronic health record (EHR) to track progress. *We will use health coaches to ensure constant patient engagement and provide the tools necessary to frequently monitor action plans and performance.*

Hypothesis and/or Specific Aims or Objectives

The primary aims and hypotheses are to:

1. Test the effectiveness of the ACP diabetes health literacy intervention to improve a range of diabetes-related outcomes among rural patients.

Compared to enhanced usual care, patients receiving ACP intervention will demonstrate:

- H_1 greater disease and treatment knowledge H_2 higher self-efficacy to manage diabetes H_3 greater adherence to self-care behaviors H_4 less diabetes-related distress H_5 improved diabetes-related quality of life H_6 better disease control (HbA1c, blood pressure)
- 2. Compared to usual care, evaluate whether the intervention reduces disparities by patient literacy level.

H₇ Limited health literacy will be associated with the above health outcomes in the enhanced usual care arm, but not in the intervention arm.

[figure not shown]
- 3. Investigate whether a threshold or gradient effect exists between the amount of follow-up counseling (number of action plans) and intervention effectiveness.

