- 4. Determine the fidelity of all intervention components, and explore any identified patient, provider (physician, nurse, health coach), and/or health system barriers to implementation.
- 5. Assess the costs associated with implementing the ACP intervention from a health system perspective.

Study Design and Procedures

We will conduct a 2-arm, patient-randomized, pragmatic trial among 750 patients in Arkansas with type 2 diabetes to test the effectiveness and fidelity of a multifaceted, health coachled, low literacy, self-management intervention to improve behavioral and clinical outcomes compared to enhanced usual care in level 3 patient centered medical homes. Enhanced usual care differs from standard diabetes care because enhanced usual care includes patient resources associated with PCMH (team-based care, electronic health records, and care coordination). Eligible, consented patients will be followed for 1 year post baseline interview. Those receiving the ACP intervention will be administered the ACP health literacy strategy at baseline, with 'frontloaded' telephone or in-person follow-up education approximately every 3 months, counseling and action-planning occurring at approximately 2 weeks, 4 weeks, and 8 weeks and then monthly between guarterly clinical visits. In-person, 'point-of-care' counseling sessions will occur guarterly, coinciding with diabetes routine clinical visits. We intentionally aimed to optimize the number of 'touch points' over 1 year, taking into account a reasonable workload for health coaches. Addressing Aim 3, which seeks to ascertain the minimum number of action plans necessary to achieve clinical diabetes goals, or an increasing benefit is seen with more touch points (no threshold). Primary outcomes include intermediary biomarkers indicative of proper disease selfmanagement (HbA1c, blood pressure, LDL cholesterol). In addition, secondary outcomes to be measured include diabetes and treatment-related knowledge, self-efficacy, disease-related distress and quality of life, activation, health behaviors and health services utilization. To determine the reliability and costs associated with delivering the intervention, we will also closely monitor the implementation process and evaluate the fidelity of the components and strategies.

		hanced Usual Care and Intervention
	STANDARD	DIABETES MEDICAL CARE
		In Both Arms
Care Management	of medical care	rting
		AND SELF-MANAGEMENT SUPPORT
	'Enhanced" Usual Care Arm	Intervention Arm

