Follow-Up	 Follow-up at scheduled clinic visits approximately every 3 months No standard, practices vary over time 	 In-person 15 min education & counseling sessions at approximately 3,6, 9, and 12 months with health coach Phone calls with health coach to inquire about progress on action plans, use motivational interviewing to problem-solve or establish new action plans Bi-weekly post-visit phone calls for first 3 months (2,4, and 8 weeks after baseline encounter) Monthly post-visit phone calls between clinic visits after 3 months (4,5,7, 8, 10, and 11 month calls) Survey data will be collected at baseline, 3 and 6 months; clinical data will be collected following baseline, 3, 6, 9, and 12 months
Clinical Integration	 Documentation in EHR with nursing note whether post visit DM counseling occurred (yes or no) and when 	 EHR tools and prompts for health coach follow-up phone calls or face-to-face meetings, documentation of call attempts Health coach received information on patients' glycemic control (HbA1c lab value at visit) prior to patient counseling session Health coach documents in EHR every month using care note function: describes and provides update for PCP detailing patient's diabetes action plans and progress towards goals Email to PCP via EHR if patient does not complete 2 consecutive action plans, identifying barriers is known, or if any concerns arise

Figure 1. Study flow chart

Study Sites

The project will engage six UAMS Regional family medicine clinics in regions of Arkansas that are underserved and rural. All clinics have implemented the Patient-Centered Medical Home (PCMH) model of care and achieved the highest level of accreditation, level 3. All regional medical centers have participated in implementation of health literacy best practices using the Agency for Healthcare Quality and Research (AHRQ)'s Health Literacy Universal Precautions Toolkit for the last two years. The majority of patients served by these clinics is low-income and there is a high rate of chronic disease in each clinic's patient population. There are approximately 2,205 total patients at these clinics with HbA1c greater than 7.5%, which denotes that an individual has perhaps not yet achieved tight glycemic control and therefore may be at elevated risk for diabetes-related complications. All clinics have agreed to participate. Letters of support from the clinic directors are included.

Preliminary Studies

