where *i* corresponds to the individual subject (*i*=1,...,*total N*), β_0 serves as an intercept, β_1 serves as the intervention effect [*I*(*ACP intervention*_i) is an indicator variable for active ACP intervention arm], β_2 represents the effect of baseline value of the corresponding outcome variable, and ϵ_i represents random error. Primary analyses will test the null hypothesis H_0 : $\beta_1 = 0$ against the twosided alternative at the 5% level of significance. Similar analyses will be employed for all relevant outcomes at three and/or six-month follow-up (to examine efficacy/effectiveness) and 12-month follow-up (to examine sustainability). Baseline variables (demographics, comorbidities, health literacy, etc.) will be explored one at a time, in turn, for association with outcome(s), and where appropriate, models will adjusted for significant baseline prognostic variables. Exploratory analyses will employ linear mixed effects models that include a fixed treatment arm, baseline value, relevant prognostic variables, and time effects along with a random subject effect in order

to account for within-subject association among outcome observations. Exploratory analyses will involve inclusion of a fixed change-point or spline term(s) to examine changes in slope over different time periods and/or higher order/interaction terms. In order to examine whether there may a difference across clinic, a random clinic effect will be examined as well, and where appropriate, subgroup analyses by clinic will be employed.

To address Aim 2 (H₇), the subjects will be classified by literacy level (lower literacy or higher literacy), and above analyses will be repeated within each arm but include an indicator for literacy group. Further, the primary model (above) will be modified to include a literacy level effect and corresponding arm-by-literacy level interaction term.

To address Aim 3, we will analyze only those subjects randomized to the ACP intervention arm. We will examine association of (a) number of contacts with each subject and (b) length of contact time, with each relevant outcome variable (H_1 - H_6) at follow-up via a linear model as above. Each model will include an intercept, baseline value for the relevant variable, and variable (a) and/or (b), along with any additional demographics/prognostic variables found relevant in Aims 1 and 2.

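### Aim 3 treats unrandomised coaching contact as a dose, and its covariate rule does not guarantee adjustment for site or for the baseline predictors of contact

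*Combined protocol and SAP*

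**What the plan says.** **The question.** In the aims section (Hypothesis and/or Specific Aims or Objectives), Aim 3 reads "Investigate whether a threshold or gradient effect exists between the amount of follow-up counseling (number of action plans) and intervention effectiveness". Study Design and Procedures adds that the aim "seeks to ascertain the minimum number of action plans necessary to achieve clinical diabetes goals".

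**The analysis.** Under Data Analysis, "To address Aim 3, we will analyze only those subjects randomized to the ACP intervention arm". The exposures are "a) number of contacts with each subject and (b) length of contact time". Each linear model contains the baseline value of the outcome, one or both exposures, and covariates carried over from the first two aims ("along with any additional demographics/prognostic variables found relevant in Aims 1 and 2"). The Aim 1 text explains how those covariates arise: baseline variables are examined singly for association with outcome, and significant ones are kept where appropriate. Clinic appears only as a random effect to be examined in exploratory work, or as a subgroup.

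**How contact arises.** The Follow-Up row of the table comparing the arms gives one schedule for all ACP patients. The coach logs described under Fidelity outcomes record whether the patient was reached in each interval and, if so, for how long. The Clinical Integration row says the coach is told the patient's "glycemic control (HbA1c lab value at visit) prior to patient counseling session".

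**The concern.** Randomisation makes the two arms comparable. It does nothing for a comparison of ACP patients who had many contacts with ACP patients who had few. Since the offer is the same for all, the spread in contacts comes mainly from patients' availability and willingness, and from differences between clinics, each of which has its own coach. Patients who pick up the phone and keep appointments may also take their medicines and watch their diet whatever the coach does. The contact slope then absorbs that difference.

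The covariate rule is not built around this problem. A variable enters because it passed a significance screen against outcome, and no step asks what predicts contact. A moderate confounder can miss the screen, and site is not assured a place. The activation index is measured but not named in the Aim 3 model.

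At stake is the Aim 3 conclusion. A slope produced by engagement could be reported as a gradient or a minimum dose of coaching.

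**Working it through.** The plan gives no figure for Aim 3, so there is none to reproduce. The check has three parts.

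**1. Is there a safeguard elsewhere?**
- Intention to treat (Data Analysis) governs analysis by randomised arm. It offers no protection inside one arm.
- Propensity score methods are mentioned, but in the list of imputation approaches for missing data, not for contact.
- No sensitivity analysis for Aim 3 is described, and nothing limits how its slope may be interpreted.

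**2. How large could a spurious slope be?**

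Inputs: n = 337 ACP patients at six months (Power and Sample Size Considerations) and a two-sided 5% test (stated for the primary analyses, assumed here for Aim 3). The correlations below are assumptions, because the documents give none.

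Let ρ be the correlation of leftover engagement with contact, and also with outcome, after the model's covariates. If contact has no effect and engagement is the only remaining link, the contact–outcome correlation is r = ρ × ρ. By Fisher's z, λ = atanh(r) × √(n − 3), with √334 = 18.28, and the rejection probability is Φ(λ − 1.96) + Φ(−λ − 1.96).

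| ρ | r | atanh(r) | λ | False dose effect |
|---|---|---|---|---|
| 0 | 0 | 0 | 0 | 5% |
| 0.2 | 0.04 | 0.0400 | 0.73 | 0.110 + 0.004 = 11% |
| 0.3 | 0.09 | 0.0902 | 1.65 | 0.378 + 0.000 = 38% |
| 0.4 | 0.16 | 0.1614 | 2.95 | 0.839 + 0.000 = 84% |

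The sign of the correlation does not matter for a two-sided test. Allowing for 12 covariates, √(337 − 3 − 12) = √322 = 17.94, and the rates become 11%, 37% and 83%.

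**3. A simulation built differently.**

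The schedule gives seven post-baseline contacts by month 6: calls at weeks 2, 4 and 8, the month-3 session, calls at months 4 and 5, and the month-6 session (3 + 1 + 2 + 1 = 7). Month-6 HbA1c was regressed on baseline HbA1c and number of contacts, with n = 337, 2,000 runs and no true dose effect. Assumptions:
- the plan's 1.9 is read as a standard deviation;
- baseline and follow-up correlate 0.5;
- engagement raises the log-odds of each contact by 0.8 per SD.

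| Engagement lowers HbA1c, points per SD | Mean slope per contact | False dose effect |
|---|---|---|
| 0 | 0.00 | 5% |
| 0.19 | −0.08 | 31% |
| 0.38 | −0.16 | 86% |
| 0.57 | −0.24 | 99% |

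In the 0.38 case, adding a proxy that correlates 0.5 with engagement moves the slope only from −0.16 to −0.13 and the false rate from 86% to 63%. Adjustment therefore helps but cannot certify a causal dose.

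**The case against.** The strongest reply has four parts.

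**The analysis text promises only an association.** That is true, and Aim 3 carries no numbered hypothesis and no power claim. But the aims and design sections speak of an effect and a necessary minimum, and nothing tells the reader to stop at association. The mismatch stands.

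**Screening on outcome is a recognised way to choose confounders.** This is partly right. A confounder must relate to outcome, and the plan's list of candidates is open, so activation, depression score or self-efficacy may enter. A reader might infer that the planned model ignores engagement altogether. The documents do not support that. Take standardised variables with a measured factor (0.4 on contact, −0.25 on outcome) and an unmeasured one (0.3 and −0.3). A slope with no covariates is then falsely significant in about 94% of simulated trials. But the measured factor would pass the plan's screen, and with it in the model the rate is about 47%. The first figure does not describe the plan. The second depends wholly on the assumed unmeasured factor.

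**Coach reaction to HbA1c is speculative.** A reader might infer from the Clinical Integration row that coaches give more time to poorly controlled patients, which would hide a true benefit. The schedule is fixed, sessions are set at 15 minutes, no rule ties contact to HbA1c, and the HbA1c model adjusts for its baseline. It is a possible further route, not a documented one, and the point does not rely on it.

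**The control arm could settle the matter.** One might predict contact from baseline variables in both arms and require an arm-by-predicted-contact interaction before claiming a dose effect. That test picks up modification of the intervention effect by those variables through any route, and H7 already expects modification by literacy. With no dose effect but direct modification of 0.25 SD by the measured factor, it rejects in about 92% of simulated trials. For a true dose effect of 0.15 SD per SD of contact its power is about 13%, or 7% if the factor's coefficient on contact is 0.2 rather than 0.4. It should not be made a condition.

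**Conclusion.** The concern holds as a limit on Aim 3. The contact slope is an unrandomised comparison, the adjustment set does not guarantee site or the baseline predictors of contact, and the stated aim asks more than the analysis can give.

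The false-positive rates of 11%, 38% and 84% illustrate the range for assumed correlations of 0.2, 0.3 and 0.4. They assume no true dose effect and engagement as the only remaining link, and they do not predict this trial's error rate. If leftover engagement is negligible, the rate is the nominal 5%.

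Two stronger readings are not supported. The randomised comparison of arms, including HbA1c at six months, does not use contact and is untouched. Nor do the documents say that the Aim 3 slope will decide how much coaching clinics provide. They say only that a minimum number of action plans is sought.

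**What to change.** 1. In every Aim 3 model, include site and the predictors of contact that the plan already collects, whatever their p-values: activation index, self-efficacy, PHQ-9, health literacy, social support and financial stress. Use baseline values. This assumes that all of these are in the baseline survey, which the analysis could confirm from the study battery.
2. State in the Aim 3 text that the result is an observational association within the ACP arm, and that it will not be reported as a causal threshold or as a minimum number of action plans needed. Bring the wording in the aims and design sections into line.

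The cost is small. With six sites (five terms) and six predictors entered as one term each, the addition is 5 + 6 = 11 degrees of freedom out of 337 patients, fewer where a variable is already in the model as the baseline outcome. No new data are needed and Aim 1 does not change. The real price is a more modest Aim 3 conclusion, which is unavoidable because unmeasured engagement remains after adjustment.
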